8.5.5 Interim Analyses

No formal interim analyses will be performed for this study.

8.5.6 Multiplicity

Not applicable.

8.5.7 Missing Values

All analyses will be based upon observed data.

[illegible]

This is an open-label trial, and therefore, site personnel, individual subjects and INOVIO or its representative trial personnel will be aware of the treatment for this trial. Randomization does not apply.

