 - IFN- γ secreting cells in peripheral blood mononuclear cells (PBMCs) by ELISpot
 - T cell phenotype and lytic potential in PBMCs by flow cytometry
4. Assessment of pro-inflammatory and immunosuppressive elements in resected tumor tissue, if available.
5. miRNA profile as related to the reduction in frequency of RRP surgical intervention, if possible.

Safety Assessment: Subjects will be followed for safety from the time of signing informed consent through Week 52, or the subject's last visit. All adverse events including SAEs, UADEs, DLTs and other AEs will be recorded. Clinically significant changes in laboratory parameters and vital signs from baseline assessments will be assessed.

Efficacy Assessment: A detailed medical history will be obtained for each subject which will include documentation of HPV-6 and/or HPV-11 RRP, a list of RRP surgeries and therapies occurring within 3 years prior to screening, and any periods of remission. Subjects must have had at least two surgical RRP interventions (including laser) in the year prior to and including Day 0, to be eligible for the trial. Subjects must require RRP intervention at the time of entry into this study and will undergo routine surgical removal of their papilloma(s) during screening, within 14 days prior to Day 0 dosing, to maximize standardization of baseline staging across subjects.

The efficacy assessment will be based upon the number of RRP surgical interventions in the 52 weeks post Day 0 compared to the number of RRP surgical interventions in the year prior to Day 0 dosing. RRP surgical interventions include laser therapies. The trial will also evaluate changes in RRP Staging Assessment over time.

Immunogenicity Assessment: The trial will explore [REDACTED] cell mediated immune responses in blood samples taken at baseline (i.e. Screening and Day 0 prior to dosing) and Weeks 6, 9, 11, 26, and 52. Tissue samples will be collected at baseline and if clinically indicated during the study.

[REDACTED]

Clinical Trial Population: Subjects with HPV-6- and/or HPV-11-associated RRP, who require at least two surgical interventions per year for the past year (minimum), for removal of associated papilloma(s). Approximately 30 adult subjects (aged 18 and older) diagnosed with Juvenile-Onset RRP (age at diagnosis <12 years) or Adult-Onset RRP (age at diagnosis ≥12 years) will be enrolled.

Inclusion Criteria; Subjects Must:

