3.4 SECONDARY ENDPOINT(S)

1. Number of RRP surgical interventions in the one year following Day 0, compared to the one year prior to Day 0.
2. Changes in Staging Assessment as measured by the RRP Staging Assessment score over time.
3. Antigen-specific cellular immune responses assessed by:
 - IFN- γ secreting cells in peripheral blood mononuclear cells (PBMCs) by ELISpot
 - T cell phenotype and lytic potential in PBMCs by flow cytometry
4. Assessment of pro-inflammatory and immunosuppressive elements in resected tumor tissue, if available.
5. miRNA profile as related to the reduction in frequency of RRP surgical intervention, if possible.

[REDACTED]

- [REDACTED]
- [REDACTED]
- [REDACTED]
- [REDACTED]
- [REDACTED]
- [REDACTED]
- [REDACTED]
- [REDACTED]

[REDACTED]

- [REDACTED]
- [REDACTED]
- [REDACTED]
- [REDACTED]
- [REDACTED]
- [REDACTED]
- [REDACTED]
- [REDACTED]

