6.14 RESTRICTIONS

Prohibited Concomitant Medications and Treatments

The following medications and treatments are prohibited:

- Long term use (≥ 7 days) of oral or parenteral glucocorticoids at a dose of ≥ 20 mg/day of prednisone equivalent; use of inhaled (nasal or bronchial), otic and ophthalmic corticosteroids are allowed;
- Disease modifying doses of anti-rheumatic drugs (e.g., azathioprine, cyclophosphamide, cyclosporine, methotrexate), and biologic disease modifying drugs such as TNF- α inhibitors (e.g. infliximab, adalimumab or etanercept) at screening and throughout the study;
- Administration of any non-study related, non-live vaccine within 2 weeks of any study treatment or within 4 weeks of any study treatment for any non-study, live vaccine (prophylactic HPV vaccination, including Gardasil) as attempted therapeutic intervention while on-study is not permitted);
- Use of bevacizumab and cidofovir should be stopped at least 3 months prior to Day 0 visit;
- Post-surgical course of anti-inflammatory medication and steroids should be avoided.

Other Restrictions

Subjects should not use alcohol or drugs that would interfere with study requirements during the course of the study and should report ALL medications/drugs taken to the investigator and/or other study personnel.

Subjects should refrain from becoming pregnant for the duration of the trial by using appropriate contraceptive measures as (See Inclusion Criteria, [Section 4.1](#)). Lapses in contraceptive use should be reported to investigator and/or other study personnel.

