8.3 STATISTICAL HYPOTHESES

No formal statistical hypothesis will be tested in this study.

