8.4 ANALYTICAL POPULATIONS

The analysis populations will be the following.

The intention to treat (ITT) population includes all subjects who are eligible.

The modified intention to treat (mITT) population includes all subjects who receive at least one dose of INO-3107.

The per-protocol (PP) population comprises subjects who receive all doses of INO-3107 and have no protocol violations. Subjects excluded from the PP population will be identified and documented prior to locking of the trial database.

The safety analysis set includes all subjects who receive at least one dose of INO-3107.

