3. GENERAL STATISTICAL METHODS

3.1. Sample Size Justification

Formal power calculation was not performed for this study, as the primary statistics are descriptive. For the safety endpoints, among n=30, we hypothesize that the true serious adverse event incidence is <12%, if no additional SAEs are observed.

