3.9. Withdrawals, Dropouts, Loss to Follow-up

A subject will be considered to have completed the trial when they have completed all study visits through Week 52. Subjects may withdraw consent at any time for any reason or be dropped from the trial at the discretion of the Investigator should any untoward effect occur. In addition, the Investigator or the Sponsor has the right to discontinue a subject from the trial at any time.

The Investigator must notify the Sponsor within 24 hours when a subject has been discontinued/withdrawn due to an AE. Any AEs and/or SAEs present at the time of discontinuation/withdrawal should be followed in accordance with the safety requirements outlined in the protocol. Subjects who are withdrawn or discontinued from the study will not be replaced.

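### The surgery endpoint has no stated rule for follow-up shorter than 52 weeks, so an early withdrawal can pass as a reduction in surgeries

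*Protocol*

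**What the plan says.** Protocol 3.4 gives the first secondary endpoint as "Number of RRP surgical interventions in the one year following Day 0, compared to the one year prior to Day 0". The Synopsis (Efficacy Assessment) and Protocol 3.7 fix the later window as the "number of RRP surgical interventions in the 52 weeks post Day 0".

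SAP 4.3.1 summarises this endpoint in two ways: a median difference with a non-parametric 95% CI, and a table of percent reduction in ranges. SAP 5 records that the median replaces the protocol's mean fold-change. SAP 4.3.1 also plans a change in surgical interval.

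SAP 4.3 makes mITT the efficacy set, with per-protocol as support. Protocol 8.4 and SAP 2.1 define mITT alike: "The modified intention to treat (mITT) population includes all subjects who receive at least one dose of INO-3107". Per-protocol requires all doses and no protocol violations.

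On missing data, Protocol 8.5.7 says "All analyses will be based upon observed data". SAP 3.10 deals only with partial dates for adverse events and medications. SAP 3.9 adds: "Subjects who are withdrawn or discontinued from the study will not be replaced". SAP 3.11 has every subject followed to the Week 52 visit, and Protocol 4.3.2 encourages subjects who stop treatment to stay on study. The visible text states no dropout rate, minimum follow-up, annualisation or person-time denominator.

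**The concern.** The two sides of the comparison do not have the same exposure. The prior year is complete for every subject because it is history. The later period is complete only for subjects who stay 52 weeks. A subject who leaves at Week 12 without surgery has been observed for less than a quarter of the period, yet a bare count gives zero surgeries and a 100% reduction.

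The visible text allows two treatments of such a subject. Keeping the truncated count biases the comparison toward benefit, and the bias grows as retention worsens. Leaving the subject out restricts the analysis to completers, which is safe only if withdrawal is unrelated to how the subject was doing. The plan does not choose between them.

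The per-protocol analysis does not settle it. The last dose is at Week 9, and completing Week 52 is not part of the definition. A Week 12 withdrawal can therefore stay in per-protocol unless the sponsor classes it as an excluding deviation under SAP 2.2.

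This is the first secondary objective, and the summary of changes for Version 3.0 describes the trial as giving an early read on efficacy to support a Phase 3 program.

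**Working it through.** **The plan's own figure.** The only sizing figure concerns safety: "among n=30, we hypothesize that the true serious adverse event incidence is <12%, if no additional SAEs are observed" (SAP 3.1). The exact two-sided 95% upper limit for 0 of 30 is 1 − 0.025^(1/30) = 11.6%, which agrees. Nothing comparable exists for the surgery endpoint, so the rest relies on stated assumptions.

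**Inputs.** From the documents: n = 30, at least 2 surgeries in the prior year, a 52-week post window, and a Week 52 visit window of ±2 weeks. Assumed: prior counts of 2 to 8 (mean 3.83), withdrawal of 0 to 30%, exit time uniform over Weeks 3 to 52, and Poisson surgeries at each subject's own prior rate. The last assumption sets the drug effect at zero and isolates truncation.

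**One subject.** Expected count = annual rate × weeks observed / 52.

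- Exit at Week 50: 2/52 = 3.8% of the count is lost.
- Exit at Week 39: 13/52 = 25% is lost.
- Exit at Week 26: 50% is lost.
- Exit at Week 11: 41/52 = 79% is lost, so 4 per year becomes 0.85.

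The chance of no surgery by Week 12 is exp(−2 × 12/52) = 63% at 2 per year and exp(−4 × 12/52) = 40% at 4 per year. Over a full year it is exp(−2) = 14% and exp(−4) = 2%.

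**All subjects.** Mean exit time among withdrawals is (3 + 52)/2 = 27.5 weeks, so each loses on average 1 − 27.5/52 = 47.1% of the expected count. With withdrawal proportion d, the expected raw ratio is 1 − 0.471d. Simulation (20,000 trials of 30 subjects, no drug effect) gives:

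| Withdrawal | 1 − 0.471d | Simulated raw ratio | Person-time ratio | Share with ≥50% reduction | Average median difference |
|---|---|---|---|---|---|
| 0% | 1.000 | 1.00 | 1.00 | 24.5% | −0.15 |
| 10% | 0.953 | 0.955 | 1.00 | 28.2% | −0.30 |
| 20% | 0.906 | 0.906 | 1.00 | 31.9% | −0.47 |
| 30% | 0.859 | 0.858 | 1.00 | 35.8% | −0.65 |

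Among withdrawn subjects alone, 62% show at least a 50% reduction. The table follows from mixing: 0.9 × 24.5% + 0.1 × 62% = 28.3%, and 0.8 × 24.5% + 0.2 × 62% = 32.0%.

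In a trial of 30, the change at 10% withdrawal is 3.7 points, or about one subject (0.037 × 30 = 1.1). At 20% it is 7.4 points, or about two (0.074 × 30 = 2.2). If the three prior-surgery strata held about 10 subjects each, one subject would move a category by 10 points.

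**With a true halving of the rate.** The raw ratio is 0.476 at 10% withdrawal and 0.454 at 20%, against a true 0.50. The share with at least a 50% reduction moves from 64.3% to 66.5% and 68.5%.

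**The case against.** The strongest reply is that this is a descriptive secondary endpoint. Protocol 8.3 says "No formal statistical hypothesis will be tested in this study", the SAP chose a non-parametric summary because of the nature of the data, and one sentence on incomplete follow-up would close the gap. That is fair about the size of the problem. It does not remove it, because a descriptive estimate is still misread if its denominator is wrong.

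Other points also stand in part:

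- **Redacted and illegible text.** The text after 8.5.7 cannot be read and several SAP 4.3.1 bullets are redacted. The contents list suggests that the unreadable block is mainly Section 8.5.8 onward, but a rule could lie there. Absence can be claimed only for visible text.
- **The interval analysis.** Change in surgical interval is time-based and partly addresses exposure. It has no visible censoring rule.
- **Retention and transparency.** Subjects are encouraged to stay, withdrawals are tabulated with reasons, and efficacy data are listed by subject. A reader could spot short follow-up, but the summary would not correct for it.
- **The median.** It dampens a few withdrawals but still shifts by 0.15 surgery at 10% withdrawal and 0.32 at 20%. The percent-reduction categories show the effect subject by subject.
- **The offset model.** It is unbiased for early exits only if the surgery rate is roughly constant over the year. Papilloma is removed within 14 days before Day 0, so early weeks may be low-risk, and an early exit could still pull the rate down.

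A reader might infer three stronger claims that the documents do not support. First, no text says that withdrawal is scored as benefit, since observed data could also mean omitting the subject. Second, a Week 50 exit is not comparable to early withdrawal: it costs at most 3.8%, and if every subject left then the raw ratio would be 0.96. Third, one might say that surgeries avoided through other RRP therapy are credited to INO-3107. The nearby text, "Use of bevacizumab and cidofovir should be stopped at least 3 months prior to Day 0 visit", is a washout before Day 0 and says nothing about counting after it.

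**Conclusion.** The point holds as a gap in the analysis rule. The visible plan compares a count over a follow-up period that can be cut short with a count over a complete year, in all dosed subjects, without saying what happens when follow-up is short. One permitted reading biases toward benefit and the other conditions on completion.

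The size is modest if retention is good. It is about 5% of the count at 10% withdrawal and about 10% at 20%, with one or two extra subjects in 30 reaching a 50% reduction. These figures rest on assumed withdrawal rates, exit times and baseline counts, and are illustrative. They also assume that withdrawal is unrelated to disease course. If subjects doing poorly leave sooner, the raw-count bias would be larger and person-time alone would not fully correct it.

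**What to change.** In SAP 4.3.1, with a cross-reference from SAP 3.10:

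- Define pre and post windows of equal length, and say which window a removal on Day 0 belongs to.
- Record each subject's days at risk in the post window and summarise follow-up time.
- Keep the median difference. Beside it, report a post/pre surgery rate ratio from a Poisson or negative-binomial model with log(days at risk) as offset, period as factor and a robust 95% CI. State that it assumes a roughly constant surgery rate, although papilloma is removed just before Day 0.
- Show subjects with incomplete follow-up in a separate row of the percent-reduction table. Counting them as not improved is an opposite bias, so it belongs in a sensitivity analysis.
- Censor the surgical-interval analysis at last follow-up.

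The cost is SAP wording, one extra model and one table row, using dates already collected. The estimate may become slightly less favourable.

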9 ETHICS

9.1 INVESTIGATOR AND SPONSOR RESPONSIBILITIES

The Investigator and Sponsor are responsible for ensuring that the clinical trial is performed in accordance with the protocol, the principles of the Declaration of Helsinki, Good Clinical Practice (GCP), and applicable regulatory requirements.

9.2 INSTITUTIONAL REVIEW BOARD (IRB)

The Investigator will undertake the trial after full approval of the protocol and adjunctive materials (e.g., informed consent form, advertising) has been obtained from the Institutional Review Board (IRB) and a copy of this approval has been received by the Sponsor.

Investigator responsibilities relevant to the IRB include the following:

- Submit progress reports to the IRB as required and request re-review and approval of the trial at least once a year during the conduct of the trial.
- Notify the Sponsor immediately of any suspected unexpected adverse drug or device events/effects.
- Notify the IRB immediately if the Sponsor notifies the Investigator about any reportable safety events.
- Obtain approval from the IRB for protocol amendments and for revisions to the consent form or participant recruitment advertisements, as required.
- Submit reports on, and reviews of, the trial and its progress to the IRB at intervals stipulated in their guidelines and in accordance with pertinent regulations and guidelines.
- Maintain a file of trial-related information (refer to trial files) that includes all correspondence with the IRB.
- Notify the IRB when the trial is completed (i.e., after the last trial visit of the final trial participant).
- After trial completion (within three [3] months is recommended) provide the IRB with a final report on the trial.

9.3 PROTECTION OF HUMAN SUBJECTS

9.3.1 Compliance with Informed Consent Regulations

Written informed consent is to be obtained from each participant prior to enrollment into the trial, and/or from the participant's legally authorized representative. The process for obtaining informed consent must also be documented in the participant's medical record. (Also refer to [section 6.2.](#))

9.3.2 Compliance with IRB Requirements

This trial is to be conducted in accordance with applicable Institutional Review Board (IRB) regulations. The Investigator must obtain approval from a properly constituted IRB prior to initiating the trial and re-approval or review at least annually. Sponsor is to be notified immediately if the responsible IRB has been disqualified or if proceedings leading to disqualification have begun. Copies of all IRB correspondence with the Investigator should be provided to Sponsor.

9.3.3 Compliance with Good Clinical Practice

This protocol is to be conducted in accordance with the applicable GCP regulations and guidelines.

9.3.4 Compliance with Electronic Records/Signatures Regulations

When applicable, this trial is to be conducted in compliance with the regulations on electronic records and electronic signature.

9.3.5 Compliance with Protocol

Participants are not required to follow special instructions specific to the IP used in this trial. Participants will be provided with Investigator emergency contact information and advised to report all AEs. While every effort should be made to avoid protocol deviations, should a deviation be discovered, Sponsor must be informed immediately. Any protocol deviation impacting participant safety must be reported to the Medical Monitor immediately.

9.3.6 Changes to the Protocol

The Investigator should not implement any deviation from or changes to the protocol without approval by Sponsor and prior review and documented approval/favorable opinion from the IRB of a protocol amendment, except where necessary to eliminate immediate hazards to trial participants, or when the changes involve only logistical or administrative aspects of the trial (e.g., change in monitors, change of telephone numbers). While every effort should be made to avoid protocol deviations, should a deviation be discovered, Sponsor must be informed immediately. Any protocol deviation impacting participant safety must be reported to the Medical Monitor immediately.

9.3.7 Vulnerable Subjects

This study prohibits the enrollment of subjects who are imprisoned, or compulsory detainment (involuntary incarceration) for treatment of either a psychiatric or physical (i.e. infectious disease) illness, as well as of children.

10 DATA COLLECTION, MONITORING AND REPORTING

10.1 CONFIDENTIALITY AND PRIVACY

A report of the results of this clinical trial may be published or sent to the appropriate regulatory authorities in any country in which the clinical trial products are legally marketed or may ultimately be marketed, but the subject's name/identity will not be disclosed in these documents. The clinical trial Sponsor, its agents, the IRB/REB/EC and regulatory authorities will have direct access to the subject's medical records for the purposes of trial-related monitoring, auditing and inspection. Appropriate precautions will be taken to maintain confidentiality of medical records and personal information.

Written Authorization and other documentation are to be obtained from each subject, and/or from the subject's legally authorized representative, prior to enrollment in the clinical trial, in accordance with all applicable laws, regulations and/or directives relating to privacy and data protection.

11 SOURCE DOCUMENTS

Source data is all information, original records or clinical findings, laboratory results, observations, or other activities in a clinical trial necessary for the reconstruction and evaluation of the clinical trial. Source data are contained in original source documents.

Examples of original source documents and data records include:

- Hospital records
- Clinical and office charts
- Laboratory notes
- Memoranda
- Subject's diaries or evaluation checklists
- Pharmacy dispensing records
- Recorded data from automated instruments
- Copies of electronic medical records (EMR) certified after verification as being accurate and complete
- Transcriptions certified after verification as being accurate and complete
- Microfiches
- Photographic negatives
- Microfilm or magnetic media
- X-rays
- Subject files and records kept at the pharmacy, at the laboratories, at the medical records facility and within information technology (IT) systems that are involved in the clinical trial

The Investigator/institution will permit clinical trial-related monitoring, audits, IRB/REB/EC review and regulatory inspections by providing direct access to source data/documents related to this clinical trial.

11.1 RECORDS RETENTION

Upon request of the Clinical Monitor, Sponsor or its agent(s), auditor, IRB/REB/EC or regulatory authority, the Investigator/institution should make available for direct access all requested clinical trial-related records.

CRFs will be provided for each subject. Subjects must not be identified by name on any CRFs. Subjects will be identified by their subject identification number (SID).

It is the Investigator's responsibility to retain clinical trial essential documents for at least two (2) years after the last approval of a marketing application in their country and until there are no pending or contemplated marketing applications in their country or at least two (2) years have elapsed since the formal discontinuation of clinical development of the IP. This retention period may be superseded by local requirements. The Sponsor will inform the Investigator/institution when these documents are no longer needed to be retained.

